11.7.6 Interim Analysis

This study is an open label study for training purposes. The data may be assessed prior to achieving the full sample size. This will be done specifically in order to assess the effect

Exalenz Bioscience Ltd.	Last update on: May1, 2016
Study Title: Clinical Study of the BreathID [®] System to train the algorithm for the ¹³ C-Octanoate Breath Test with or without the ¹³ C-Methacetin Breath Test (OBT and MBT respectively) for correlation with histological findings of Non-Alcoholic Fatty Liver Disease (NAFLD)	Protocol No.: NASH-EX-1114
	Version: 1f
Document N^o: CSD00080	Page 34 of 61

of confounding factors on the correlation between OBT with or without MBT and binary diagnosis of biopsy proven NASH or NAFL. If any confounding factor shows significantly different correlation than the rest of the population, the study population may be increased to up to 400 patients.

11.7.7 Pooling

Subgroup analysis of the primary performance endpoint by center via a regression model will be used to evaluate the poolability of the results. If the variable by center analysis is found significant, the reason for this will be further explored and rationalized. This evaluation may include demographic features, symptoms at presentation, clinical and treatment history, and center comparability in the features found to be associated with the primary efficacy variable

11.7.8 Handling of Missing Data

The study variables cannot be evaluated for patients for whom OBT or MBT results or liver biopsy results are not available and therefore these subjects will be left out of the primary efficacy analysis. Demographic clinical characteristics and safety data of patients with missing data will be compared to patients with complete data.

11.7.8.1 Procedure

After all the relevant data is entered into the database, a soft lock to the database will be performed. The study statistician will perform the assessment of the primary and safety endpoints.

11.7.8.2 Decision Rules

Stop the study in case of severe safety concern.

Exalenz Bioscience Ltd.	Last update on: May1, 2016
Study Title: Clinical Study of the BreathID [®] System to train the algorithm for the ¹³ C-Octanoate Breath Test with or without the ¹³ C-Methacetin Breath Test (OBT and MBT respectively) for correlation with histological findings of Non-Alcoholic Fatty Liver Disease (NAFLD)	Protocol No.: NASH-EX-1114
	Version: 1f
Document N^o: CSD00080	Page 35 of 61

12 STUDY PROCEDURES

12.1 General

1. The study will be conducted in compliance with this protocol, in concordance with GCP standards, and applicable regulatory requirements.
2. The study design is: cross-sectional, enrolling patients in a consecutive manner per site, so as to prevent any bias.
3. Patients will sign a consent/assent form prior to study participation
4. An eCRF will be completed for each subject.
5. The raw data will be saved on the *BreathID*[®] device.
6. All patients undergoing liver biopsy to rule-out or confirm NAFLD, within 6 months prior to breath tests and within 1 month after first breath test, should be considered for enrollment. If the biopsy is done on the day of one of the breath tests, the breath test must precede the biopsy.
7. Biopsy slides of enrolled patients may undergo high-resolution scanning to simplify central reading and filing.
8. All tissue slides or their respective scans if relevant, will be read twice; once by the local (study site) pathologist and once by the central reading laboratory. In case of discrepancy the central reading results prevail. The characteristics to record for each sample are specified within Appendix II to this protocol. All parameters will be entered into the study eCRF.
9. Any adverse events will be recorded according to GCP ICH guidelines. Section 0 below¹⁵ below relates to the reportable and non-reportable SAEs.
10. All investigators will be blinded to the OBT and MBT results until the end of the study recruitment. This is to ensure that OBT and MBT results will not affect the current patient management. Hard copies of the device printouts will be stored separately from the other source data and the section within the eCRF containing the

Exalenz Bioscience Ltd.	Last update on: May1, 2016
Study Title: Clinical Study of the BreathID [®] System to train the algorithm for the ¹³ C-Octanoate Breath Test with or without the ¹³ C-Methacetin Breath Test (OBT and MBT respectively) for correlation with histological findings of Non-Alcoholic Fatty Liver Disease (NAFLD)	Protocol No.: NASH-EX-1114
	Version: 1f
Document N^o: CSD00080	Page 36 of 61

breath tests results will remain inaccessible to the treating physician (i.e. the investigator login will keep this section hidden).

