10.8 Expected Duration of Recruitment

The enrollment to the study is planned for a duration of approximately 6-12 months.

Exalenz Bioscience Ltd.	Last update on: May1, 2016
Study Title: Clinical Study of the BreathID [®] System to train the algorithm for the ¹³ C-Octanoate Breath Test with or without the ¹³ C-Methacetin Breath Test (OBT and MBT respectively) for correlation with histological findings of Non-Alcoholic Fatty Liver Disease (NAFLD)	Protocol No.: NASH-EX-1114
	Version: 1f
Document N^o: CSD00080	Page 31 of 61

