11 STATISTICAL CONSIDERATIONS

11.1 Study Design and Objectives

This is a multicenter, non-randomized, open-label, cross-sectional comparative exploratory study comparing OBT with or without MBT values to histologic findings from liver biopsy associated with NAFLD.

This study will be used to train an algorithm using OBT with or without MBT with or without other commercially available biomarkers and to select a cut-off to determine correlation with histological findings of NALFD and determine clinical outcome at 18 and 36 months, if available.

The modeled algorithm will be validated in a separate study.

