11.3 Secondary efficacy endpoint

Correlation between OBT with or without MBT and clinical course (i.e. clinical outcome: liver decompensation events etc.) at 18 and 36 months post the last breath test performed (visit / phone). NOTE: Patients undergoing intervention for NASH / NAFLD, including both approved and experimental approaches prior to the defined time points will be terminated hence will not be evaluated for this endpoint.

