12.6 Visit 5: Clinical Follow-Up 18 Months

18 months \pm 4 weeks post the last breath test performed a phone / in-person visit will be conducted in order to assess major clinical events (i.e. Death, liver transplant, liver decompensation events including: ascites, hepatic encephalopathy, variceal bleeding, hepato-renal syndrome, spontaneous bacterial peritonitis). In addition, the patient's clinical records will be reviewed.

NOTE: Patients undergoing intervention for NASH / NAFLD, including both approved and experimental approaches prior to the defined time points will be terminated hence will not be evaluated for this endpoint.

Exalenz Bioscience Ltd.	Last update on: May1, 2016
Study Title: Clinical Study of the BreathID [®] System to train the algorithm for the ¹³ C-Octanoate Breath Test with or without the ¹³ C-Methacetin Breath Test (OBT and MBT respectively) for correlation with histological findings of Non-Alcoholic Fatty Liver Disease (NAFLD)	Protocol No.: NASH-EX-1114
	Version: 1f
Document N^o: CSD00080	Page 41 of 61

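### The investigator blind to breath-test results ends with recruitment, before any planned 18- or 36-month outcome visit

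*Combined protocol and SAP*

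**What the plan says.** Section 12.1, item 10 sets the blind: "All investigators will be blinded to the OBT and MBT results until the end of the study recruitment". Its stated reason is patient care: "This is to ensure that OBT and MBT results will not affect the current patient management". The item then describes two controls. Printouts are filed apart from the other source data, and the eCRF section with the "breath tests results will remain inaccessible to the treating physician (i.e. the investigator login will keep this section hidden"). Neither control has a stated end date. Item 5 of the same section adds: "The raw data will be saved on the" BreathID device, with no access rule of its own.

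On timing, section 10.8 says: "The enrollment to the study is planned for a duration of approximately 6-12 months". Under 12.6 and 12.7, at 18 months ± 4 weeks and 36 months ± 8 weeks "post the last breath test performed a phone / in-person visit will be conducted in order to assess major clinical events", and clinical records are reviewed as well. Sections 9.4.2 and 11.3 make the correlation of the breath tests with clinical course at these two times the secondary efficacy endpoint. Patients who have an intervention for NASH or NAFLD, "including both approved and experimental approaches prior to the defined time points will be terminated hence will not be evaluated for this endpoint". Section 11.1 qualifies the use of this follow-up: the study will "determine clinical outcome at 18 and 36 months, if available".

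**The concern.** The breath test is the predictor in the secondary endpoint. If the person who records the outcome, or who decides on treatment, knows the test result, two routes to bias open.

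- **Ascertainment.** The listed events are death, transplant and five kinds of decompensation. Death and transplant leave little room for judgement. Ascites and encephalopathy leave more, particularly when the visit may be by telephone. The protocol describes neither a blinded outcome assessor nor adjudication.
- **Removal from the endpoint.** Treated patients are terminated and not evaluated. If a known breath result influences who is treated, inclusion in the analysis depends on the variable under study.

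Item 10 recognises that results could influence management, but it guards against this only while recruitment is open.

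**Working it through.** The plan gives no figure of its own on this point, so the check is a comparison of dates.

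**Inputs.** Recruitment R = 6 to 12 months (10.8). Visit 5 at 18 months ± 4 weeks (12.6). Visit 6 at 36 months ± 8 weeks (12.7). MBT from 48 hours to 30 days after the OBT (12.4). One month is taken as 30.44 days.

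**Visit windows after the last breath test**
- Visit 5: 18 ± 28/30.44 = 18 ± 0.92, so 17.08 to 18.92 months.
- Visit 6: 36 ± 56/30.44 = 36 ± 1.84, so 34.16 to 37.84 months.

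**Gap from the end of recruitment to the first possible visit** (first patient's last breath test at month 0)

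| Recruitment | First Visit 5 | First Visit 6 |
|---|---|---|
| 6 months | 17.08 − 6 = 11.1 months | 34.16 − 6 = 28.2 months |
| 12 months | 17.08 − 12 = 5.1 months | 34.16 − 12 = 22.2 months |

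Every gap is positive, so 0% of either visit falls inside the stated blind. An MBT given 30 days after the OBT moves the visits later by 30/30.44 = 0.99 month and widens the gaps.

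**Share of the follow-up window outside the blind.** This matters for treatment decisions, which can come at any time. Assume uniform enrolment with the last breath test at enrolment. Mean blinded time is then R/2, which is 3 months for R = 6 and 6 months for R = 12.
- 18-month window: 1 − 3/18 = 83%; 1 − 6/18 = 67%.
- 36-month window: 1 − 3/36 = 92%; 1 − 6/36 = 83%.

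**Sensitivity to slow recruitment.** Some 18-month visits are covered only if recruitment runs beyond about 17.1 months. Section 11.5 allows enlargement from 200 to 400 patients without stating a duration. If 400 patients were recruited at the rate planned for 200, recruitment would take 12 to 24 months. For R = 24 (an assumption), the share of Visit 5 inside the blind is:
- earliest date in the window: (24 − 17.08)/24 = 28.8%
- nominal date: (24 − 18)/24 = 25.0%
- latest date in the window: (24 − 18.92)/24 = 21.2%

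The share for Visit 6 remains 0%, because 34.16 > 24.

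These percentages are shares of visits and calendar time. They do not measure the size of any bias.

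**The case against.** The strongest reply is that the text does not show an unblinding. Nowhere does the protocol say that results are released when recruitment closes, and the eCRF and printout controls carry no end date. They could be read as lasting indefinitely, which would deal with most of the problem. That reading is possible, but it conflicts with the opening sentence of the same item, which gives an explicit end. The controls may simply be how that limited blind is applied. On either reading the item needs an end date that fits the follow-up.

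Other points on that side carry weight:
- No trained score or cut-off exists while recruitment is open, so an investigator has no rule for acting on a raw result.
- Each patient has a biopsy that the site's own pathologist reads. Treatment, and hence removal, driven by biopsy severity would remain under full blinding.
- Most of the listed events are hard, and the record review gives a source beyond the interview.
- The endpoint is secondary and exploratory, section 11.7.5 describes performance analysis against histology only, and the algorithm is to be validated in a separate study.

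These points limit how much bias is likely. They do not close the gap. On device data, item 10 is not limited by medium and so already covers the device while the blind lasts; what is missing is cover after that.

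**Conclusion.** The concern holds. With recruitment at the planned 6-12 months, the stated blind covers none of the 18- or 36-month assessments and lapses 5.1 to 11.1 months before the first of them. Assuming uniform enrolment, 67-83% of the 18-month window and 83-92% of the 36-month window lie outside it. Whether the eCRF block outlasts the blind cannot be settled from the text.

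Bias in the correlation between breath test and outcome is possible, not shown: investigators would have to see the results and act on them. The effect is confined to the secondary endpoint. The primary endpoint rests on central histology, which the length of the investigator blind does not touch; the protocol's silence on whether the central reader is blinded is a separate matter. The change is worth making because it is cheap, and it should be made before recruitment closes because unblinding cannot be undone.

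**What to change.** In section 12.1, item 10, replace the end of recruitment as the end of the blind with the point at which *the last patient has completed Visit 6 or been terminated*. At minimum, blind each patient's results until that patient's own Visit 6 or termination. Add one sentence stating that the hidden eCRF section, the separately filed printouts and access to raw data on the BreathID device are all covered for that same period.

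This protects both outcome recording and later treatment decisions. A blinded assessor alone would protect only the first.

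The cost is one reworded clause and one added sentence. The eCRF block and the separate filing of printouts already exist, and no visit or procedure changes. The downside is that sites wait longer for investigational results, and data on devices held at sites must be kept from investigators through about three years of follow-up.

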12.2 Visit 1: Screening / enrollment

1. Pre-screening for inclusion / exclusion criteria
2. As part of eligibility, biopsy slides should be "up to standard" according to the quality requirements specified within Appendix II to this protocol. (Biopsy quality requirements are as follows: Unfragmented needle core \geq 20mm length with \geq 10 portal tracts is recommended, according to the AASLD practice guidelines or equivalent.)
3. A minimum of Hematoxyline & Eosine (H&E) and Masson's trichome stained slides should be available. Additional optional stains include: Chromotrope Aniline blue (connective tissue), Prussian blue (iron storage), Sirius red stain (for fibrosis) and SMA will be filed if available. Additional unstained slides are recommended.
4. Histology slides or their respective scans, will be assessed by both the local pathologist and a central reader according to the parameters listed within Appendix II to this protocol. In case of significant differences in the assessment the central reader will always prevail.
5. Consenting patient.
6. Complete study eligibility and enrollment.
7. Physical or high resolution scanned slides sent to local and central reading according to Appendix II.

12.3 Visit 2: ¹³C-Octanoate Breath Test (OBT)

1. Female patients of childbearing age meeting all criteria will undergo pregnancy test if not available from the past 7 days. Abstinence or oral contraceptives are requested until completion of MBT (second breath test).

Exalenz Bioscience Ltd.	Last update on: May1, 2016
Study Title: Clinical Study of the BreathID [®] System to train the algorithm for the ¹³ C-Octanoate Breath Test with or without the ¹³ C-Methacetin Breath Test (OBT and MBT respectively) for correlation with histological findings of Non-Alcoholic Fatty Liver Disease (NAFLD)	Protocol No.: NASH-EX-1114
	Version: 1f
Document N^o: CSD00080	Page 37 of 61

2. OBT will be performed within 6 months post liver biopsy.
3. Medical History including the following:
 - a. Demographics
 - b. Detailed medical history including liver directed and other concomitant diseases (cardiovascular, respiratory, renal and neurological), presentation, interventions, etiology, habits etc.
 - c. Imaging results,- (if available) Ultrasound, CT and/or MRI, (liver outline, vasculature, evidence of fat etc.), imaging of major hepatic vessels, pancreas, intestines, and liver volume
 - d. Other assays: e.g. HVPG
 - e. Most recent laboratory blood test results within 6 months.
 - f. Concomitant medications
4. Physical examination (targeting liver related findings) including liver related clinical scoring.
5. In preparation for the OBT:
 - a. Eight (8) hours fasting prior to OBT including all PO morning medications except for beta blockers. Diabetic patients that are driving should test their blood sugars to rule out hypoglycemia and respond accordingly.
 - b. No general anesthesia or sedation within 24 hours prior to OBT
 - c. No alcohol within 24 hours prior to OBT
 - d. Patient should be symptom free of any prior intervention (e.g. biopsy)
6. Within one hour prior to the OBT blood will be drawn for the following panels (note the relevant remarks):
 - a. Insulin and Glucose
 - b. Complete Blood count (WBC, Hemoglobin, Platelets) and CRP
 - c. Coagulation: PT (INR)

Exalenz Bioscience Ltd.	Last update on: May1, 2016
Study Title: Clinical Study of the BreathID [®] System to train the algorithm for the ¹³ C-Octanoate Breath Test with or without the ¹³ C-Methacetin Breath Test (OBT and MBT respectively) for correlation with histological findings of Non-Alcoholic Fatty Liver Disease (NAFLD)	Protocol No.: NASH-EX-1114
	Version: 1f
Document N^o: CSD00080	Page 38 of 61

- d. Renal panel and electrolyte panel (BUN, creatinine, electrolytes (Na⁺ and K⁺),
- e. Collection of 4ml of blood for serum and freezing for storage (no preservative tube) where possible.
- f. Hepatic panel (AST, ALT, alkaline phosphatase, GGTP, total bilirubin, direct bilirubin, serum albumin and total protein) - if not available from within 3 months
- g. Additional Coagulation Panel (PTT, fibrinogen) - if not available from within 3 months
- h. Total calcium, PO₄ (phosphate corrected), magnesium - if not available from within 6 months
- i. Lipid profile and HbA1c - if not available within 6 months
- j. Thyroid Panel - if not available within 12 months
- k. Other assays where routinely practiced; (optional): Adiponectin + Leptin + IL6 + CK18, TNF α , C-peptide

NOTE: if possible more than just the essential blood panels (sections a. to d.) will be collected adjacent to the OBT.

7. ¹³C-Octanoate Breath Test:

NOTE: Expected warm-up time for the device to be ready to measure patient's breath is up to 90 minutes. Ensure the device is turned on at least 2 hours prior to scheduled patient visit.

The breath test is performed automatically while the patient is connected to the device using a nasal cannula. The test is of 2 phases: baseline and the sampling phase separated by the administration of the test substrate. The 2 phases' durations are up to 30 and up to 60 minutes respectively.

For more information regarding the OBT procedure please refer to Section 5 of the Investigator's Brochure.

8. Adverse events recording until the subject completes the protocol.

NOTE: Any AEs reported that are possibly or probably related to the use of the product or related to the procedure within 36 months post OBT or until subject termination will be followed until resolution and if laboratory work is done secondary to AEs and

Exalenz Bioscience Ltd.	Last update on: May1, 2016
Study Title: Clinical Study of the BreathID [®] System to train the algorithm for the ¹³ C-Octanoate Breath Test with or without the ¹³ C-Methacetin Breath Test (OBT and MBT respectively) for correlation with histological findings of Non-Alcoholic Fatty Liver Disease (NAFLD)	Protocol No.: NASH-EX-1114
	Version: 1f
Document N^o: CSD00080	Page 39 of 61

found abnormal, these tests will be followed until normalization or stabilization.

9. Diabetic patients will be followed throughout the entire visit and should be instructed to resume their medication immediately after the breath tests.

12.4 Visit 3: ¹³C-Methacetin Breath Test (MBT)

1. MBT will be conducted within 6 months post liver biopsy and within 30 days of the OBT but not less than 48 hours post OBT.
2. In preparation for the MBT:
 - a. Eight (8) hours fasting prior to MBT including all PO morning medications except for beta blockers. Diabetic patients that are driving should test their blood sugars to rule out hypoglycemia and respond accordingly.
 - b. No smoking on the day of the MBT
 - c. No paracetamol (acetaminophen) based medications within 24 hours prior to MBT
 - d. No general anesthesia or sedation within 24 hours prior to MBT
 - e. No alcohol within 24 hours prior to MBT
 - f. Patient should be symptom free of any prior intervention (e.g. biopsy)

3. ¹³C-Methacetin Breath Test:

NOTE: Expected warm-up time for the device to be ready to measure patient's breath is up to 90 minutes. Ensure the device is turned on at least 2 hours prior to scheduled patient visit.

The breath test is performed automatically while the patient is connected to the device using a nasal cannula. The test is of 2 phases: baseline and the sampling phase separated by the administration of the test substrate. The 2 phases' durations are up to 30 and up to 60 minutes respectively.

Exalenz Bioscience Ltd.	Last update on: May1, 2016
Study Title: Clinical Study of the BreathID [®] System to train the algorithm for the ¹³ C-Octanoate Breath Test with or without the ¹³ C-Methacetin Breath Test (OBT and MBT respectively) for correlation with histological findings of Non-Alcoholic Fatty Liver Disease (NAFLD)	Protocol No.: NASH-EX-1114
	Version: 1f
Document N^o: CSD00080	Page 40 of 61

For more information regarding the OBT procedure please refer to Section 5 of the Investigator's Brochure.

4. Adverse events recording until the subject completes the protocol.
NOTE: Any AEs reported that are possibly or probably related to the use of the product or related to the procedure within 36 months post last breath test performed or until subject termination will be followed until resolution and if laboratory work is done secondary to AEs and found abnormal, these tests will be followed until normalization or stabilization.
5. Diabetic patients will be followed throughout the entire visit and should be instructed to resume their medication immediately after the breath tests.

12.5 Visit 4: 48 safety hours phone call

1. 48 hours post the last breath-test (presumably MBT) a safety oriented phone call will be conducted.
2. All adverse events post OBT will be recorded until the subject completes the protocol.
NOTE: Any AEs reported that are possibly or probably related to the use of the product or related to the procedure within 36 months post last breath test performed or until subject termination will be followed until resolution and if laboratory work is done secondary to AEs and found abnormal, these tests will be followed until normalization or stabilization.
3. This visit determines the last safety reporting point to be reported in to the safety endpoint.

